prevention. Barriers such as lack of convenient access and economic instability have a major impact on retention in care for persons living with HIV (PLWH). The aim of this project is to evaluate the extent to which integrated community-based HIV care with group microfinance affects retention in care and viral suppression among PLHIV in rural western Kenya. We will use a cluster randomized controlled intervention design to randomize at least 40 existing microfinance groups (with a majority of members who are living with HIV) to receive microfinance plus either (A) integrated community-based care, or (B) standard care. We will also recruit a matched control group (C), receiving standard care without participation in microfinance activities. The hypothesis is that integrated communitybased care, within group microfinance, will improve viral suppression and retention in care compared to microfinance with standard of care and to standard of care alone. We will use qualitative and quantitative mediation analysis to evaluate mechanisms through which microfinance and ICB care impact outcomes, and analyze incremental cost-effectiveness of the intervention in terms of cost per HIV suppressed person-time, cost per patient retained in care, and cost per disability-adjusted life-year saved.

Primary Objective: The primary objective of this project is to

demonstrate the effectiveness of an integrated community-based care approach for improving viral suppression and related outcomes among HIV-positive individuals participating in

microfinance groups.

Endpoints: Primary Endpoint: The primary endpoint for this study will be

achievement of viral suppression (HIV-RNA < 400

cp/mL) at 18 months.

Secondary Endpoints: A secondary endpoint will be retention in care,

defined as the proportion of scheduled visits that were attended during the study period. Other secondary endpoints will be absolute mean change in systolic blood pressure and absolute mean change in HbA1c level from 0 to 18 months.

Study Population: The population eligible for study participation will include HIV-positive

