3.4.2 Power calculation

For the sample size calculations, the standard deviation of the group size was set to 5, type-one error rate to 0.05, a two-sided test, and the intra-class correlation coefficient to 0.05. Based on studies of the effect of financial interventions we expect at least 15% increase in viral suppression between MF+ICB and MF+SOC, between MF+SOC and SOC only, and between MF+ICB and SOC only groups. ^{13,45} The power calculations used viral suppression in MF+SOC ranging from 20 to 50% and, as in the BIGPIC trial, accounted for 15% dropout. ⁴³ For all the different scenarios considered, the power to detect a 15% increase in viral suppression was greater than 80% for testing all three hypotheses.

4. Aim 1 RCT Methods: Enrollment

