8.3 Aim 2 statistical analyses

Quantitative mediation analyses. We will use causal mediation analysis to evaluate the importance of causal pathways between microfinance and integrated community-based care and viral suppression and retention. We will use the data described in Aim 1 collected at baseline, 9-month, and 18-month follow-up visits. The primary analysis will focus on two main mediators: household economic conditions and access to care. We will estimate the mediation effect of each mediator separately using the difference method and account for multiple comparisons using a Bonferroni correction. The generalized linear models needed to implement the difference method will adjust for key confounders such as education, location, gender, and age. We will perform a sensitivity analysis of the assumption of no unmeasured mediator-outcome confounders. As a secondary analysis, we will use causal mediation analysis to evaluate the mediation effect of food security, social support, and HIV-related stigma. We hypothesize that there will be similar improvements in household economic conditions between the two MF and MF+ICB groups, but that barriers in access to care will be more improved in the MF+ICB arm. Differences in these mechanisms will provide important information regarding the additive impact of integrated community-based care on the hypothesized relationships.

Qualitative mediation analyses. Text from the n=50 interviews will be coded into a hierarchical, branching structure in which broad concepts are first identified, along the domains identified in the interview guides and our conceptual model, and then themes and variations within those themes will be defined and text will be labeled according to these definitions. Coded data from intervention participants will be compared to identify mechanisms through which MF and community-based care impacted retention in HIV care and adherence to ART, and the additive impact of the community-based care delivery in the intervention group. Specifically, data will compare between the intervention arms the added benefits of community-based care, beyond those relevant to both groups from the MF activities. We will triangulate findings using data from the qualitative study to explain and expand on findings from the quantitative mediation analysis.

9. Aim 3. Cost-effectiveness analysis

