Aim 3 will perform a cost-effectiveness analysis to test the working hypothesis that microfinance groups with integrated community-based care (MF+ICB) are more cost-effective compared to microfinance without ICB (MF+SOC) and standard care (SOC).

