9.1 Aim 3 procedures

Costs attributable to the intervention will be collected during the randomized controlled trial (Aim 1) for each relevant study period at 6, 12, and 18 months. Costs will be recorded using a cost tracking tool developed specifically for this study. We will estimate differences in the intervention arms (MF+ICB and MF+SOC) and the controls (SOC). The differences in costs among the control and intervention arms will be defined as the incremental costs (Δ C). Cost estimates for the controls will be obtained from

AMPATH's existing electronic medical records (AMRS) as well as accounting and administrative records, and interviews with n=5 key informants such as administrative directors, comptroller, and local managers. In particular, we will use project and administrative records to conduct a cohort-based, microcosting approach. We will assess cost differences between the control and intervention arms including the total costs of the medications (ART, NCD control, etc.), as well as transportation and wait time costs. For each participant, we will review the AMRS to determine the actual utilization of ART, non-ART drugs, laboratory tests used, and clinic visits for each patient.

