9.2 Aim 3 statistical analyses

Costs will be calculated from three distinct perspectives. First, we will take the perspective of AMPATH as a provider of care. Total costs will be defined as the sum of fixed and variable costs. Variable costs for each patient will be calculated by multiplying the number of units of each good or service used by the unit cost. Costs of ART will be obtained from the official AMPATH/PEPFAR supplier in Kenya. Unit costs for non-ARV drugs will be estimated by reviewing invoices and interviewing key informants. Clinical care unit costs will be estimated by multiplying the time of the clinical interaction (based on time motion logs) by the amount spent on staff salaries by level (medical officer, nurse, etc.) and overhead. All costs incurred by the project, not directly attributable to individual participants will be considered as part of the fixed costs. These are usually costs that are exercised regardless of the volume of participants (cleaning, maintenance, utilities, etc.). Fixed costs will also include any equipment bought (new testing machines, motorcycle, rent/space costs, etc.) which will be discounted at a rate of 5% per year to account for depreciation. Total fixed costs will be allocated to all the participants proportionally. Second, we will take into account costs from the patients point of view, which will include time and transport costs to the place where care is received (i.e., the clinic for the SOC vs. the microfinance meeting place for the MF+ICB group). Third, we will perform a potential cost-saving estimation from the point of view of government and donors where financial outlays are compared into the future to gauge the extent to which the proposed intervention can be financially self-sustained.

Effectiveness: We will use the changes in primary and secondary outcomes, as explained in Aim 2; namely: viral suppression and retention-in-care. The incremental effectiveness (ΔE) will be defined as the difference in outcomes between the SOC and the intervention groups.

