Incremental Cost-Effectiveness Ratio (ICER) will be defined as incremental cost over incremental effectiveness ($\Delta C/\Delta E$). In addition, we will model incremental costs per disability-adjusted life year (DALY) averted to make the results comparable to the international cost-effectiveness literature. We will model the effects over the life span using the Sullivan method discounting future effects. For the net benefits estimation, we will transform costs into constant 2018 USD using the Kenyan consumer price index and the international average exchange rate to convert from Kenyan shillings (KES) to USD. We will compare the cost per DALY saved to the Kenyan income per capita (GDPpc) and deem the intervention extremely cost-effective if \$/DALY is less than 1*GDPpc, highly cost-effective if \$/DALY is less than 3*GDPpc.

Sensitivity Analysis: We will use sensitivity analyses to describe the scope and nature of the inherent uncertainties surrounding the cost-effectiveness estimates. Each parameter in the model will be varied across a plausible range of in a series of one-way sensitivity analyses and those that exhibit the largest magnitude of influence either in effects, costs, or the resultant cost-effectiveness ratio, will be varied together in multi-way sensitivity analyses. In addition, we will conduct threshold analysis, whereby we will point out the values at which the intervention options may no longer be cost-effective; we will use a probabilistic uncertainty analysis for the variables that have an underlying probability distribution.

The final cost-effectiveness results will be measured with incremental cost effectiveness ratios comparing the SOC with each of the additional interventions. In addition, given that each of the innovations may have an optimal level of scale and diffusion, and potential cost savings from the perspective of each of the actors. To estimate return on investment we will use a cost-utility approach that we have successfully used for HIV testing and can be adopted for HIV treatment retention interventions.

10. Protection of human subjects

This study involves research that is classified as non-exempt human subjects research. All procedures of this research will be conducted in accordance with 45 CFR Part 46 and will be approved by the Moi University School of Medicine IRB (the IRB of record) and the Brown University Institutional Review Board (the prime award recipient).

10.1Risks to human subjects

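### Aim 3 hypothesises that MF+ICB is more cost-effective than MF+SOC as well as SOC, but plans ICERs only against the non-randomised SOC arm and names no comparator for the GDP-per-capita label

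*Combined protocol and SAP*

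**What the plan says.** The opening of section 9 sets the Aim 3 hypothesis with two comparators: "microfinance groups with integrated community-based care (MF+ICB) are more cost-effective compared to microfinance without ICB (MF+SOC) and standard care (SOC").

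Section 9.1 counts MF+ICB and MF+SOC as the intervention arms and SOC as the controls. It then defines cost increments: "The differences in costs among the control and intervention arms will be defined as the incremental costs".

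Section 9.2 says that incremental effectiveness "will be defined as the difference in outcomes between the SOC and the intervention groups". The ICER is the ratio of these two increments, and the final results are "incremental cost effectiveness ratios comparing the SOC with each of the additional interventions". On thresholds, section 9.2 states: "We will compare the cost per DALY saved to the Kenyan income per capita (GDPpc) and deem the intervention extremely cost-effective" below one GDP per capita per DALY, with a second label below three. No comparator is attached to either label.

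The Summary says that the study will "analyze incremental cost-effectiveness of the intervention in terms of cost per HIV suppressed person-time" and names no comparator. None of the eleven addendum items changes Aim 3.

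Elsewhere, MF+ICB versus MF+SOC is the primary contrast (section 7.2; addendum item 10), and section 8.3 expects its mechanism comparison to give "important information regarding the additive impact of integrated community-based care". Section 3.2 describes Arm C (SOC) as a non-randomised matched comparison.

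**The concern.** The hypothesis has two parts, and the planned ratios address only one of them directly. The part left out asks what community care adds to groups that already have microfinance. It is also the part that randomisation protects.

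Both planned ICERs instead rest on Arm C. Its matching was loosened during the trial: addendum item 8 dropped county and facility, so that about 90 Busia members were matched to 30 patients in Trans Nzoia. An MF+ICB versus SOC ratio also bundles the effect of microfinance with that of community care.

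At stake is the conclusion that a funder would read. A cost-per-DALY label for MF+ICB against SOC need not be the label for adding community care to existing groups, and the plan does not say which of the two its label describes.

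**Working it through.** The documents give no cost, DALY or ICER figure for Aim 3, so there is no stated result to reproduce. The check is a reading of the text followed by algebra.

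**Which contrasts are defined**

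- Hypothesis (section 9): MF+ICB versus MF+SOC, and MF+ICB versus SOC.
- Cost increment (9.1): among control and intervention arms. This is loose enough to include MF+ICB versus MF+SOC.
- Effect increment (9.2): SOC versus the intervention groups only.
- Final ICERs (9.2): SOC versus each other option only.

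SOC cannot be read here as MF+SOC, because section 9.1 places MF+SOC among the intervention arms. A cost increment with no matching effect increment does not make an ICER.

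**What the planned quantities determine**

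Let EA and EB be the effects of MF+ICB and MF+SOC against SOC, RA and RB their ICERs against SOC, and k = EB/EA. Then

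ICER(MF+ICB vs MF+SOC) = (RA·EA − RB·EB)/(EA − EB) = (RA − k·RB)/(1 − k).

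The value of k cannot be recovered from RA and RB alone. It can be recovered from the increments behind them: with simple arm differences, (A − C) − (B − C) = A − B, and Arm C cancels. If the two SOC contrasts were instead adjusted separately, as addendum item 10 does for suppression, the cancellation need not be exact.

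**Sensitivity, not prediction**

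Section 3.4.2 expects "at least 15% increase in viral suppression between MF+ICB and MF+SOC, between MF+SOC and SOC only". Read as percentage points at the minimum, EB = 15 and EA = 15 + 15 = 30, so k = 0.5 and the ICER is 2·RA − RB. The 30 is my sum; section 3.4.2 itself says only at least 15% for MF+ICB over SOC. RB is assumed throughout. The randomised ICER as a multiple of RA is:

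| k | RB = 0 | RB = 0.5 RA | RB = RA | RB = 1.5 RA |
|---|---|---|---|---|
| 0.25 | 1.33 | 1.17 | 1.0 | 0.83 |
| 0.5 | 2.0 | 1.5 | 1.0 | 0.5 |
| 0.75 | 4.0 | 2.5 | 1.0 | −0.5 |

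The negative cell means that MF+ICB costs less than MF+SOC and achieves more. If k = 1 and MF+ICB costs more, MF+ICB is dominated by MF+SOC while RA stays finite.

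**Effect on the label**

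Take RB = 0, k = 0.5 and DALYs proportional to suppression. The factor is then 2. An RA between 3/2 = 1.5 and 3 GDP per capita meets the upper limit against SOC, while the randomised ratio (3 to 6) does not. An RA between 1/2 = 0.5 and 1 meets the lower limit against SOC, while the randomised ratio (1 to 2) does not.

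**Direction**

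For 0 < k < 1, the randomised ICER exceeds RA exactly when RB < RA. When RB > RA, MF+SOC is extendedly dominated. A full incremental analysis then compares MF+ICB with SOC and returns RA, the ratio already planned. The label is therefore too favourable only if RB < RA.

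**How far the illustration reaches**

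Section 3.4.2 assumed 20 to 50% suppression in MF+SOC. Addendum item 10 says that a high overall rate of suppression was later known, without giving it. A 15-point gain cannot fit above an MF+SOC rate of 100 − 15 = 85%, so k = 0.5 may not describe this trial.

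**The case against.** The strongest reply is that nothing is really missing. Each SOC-based ICER needs its own cost and effect increments, so the MF+ICB versus MF+SOC increments and simple dominance follow by subtraction. Ranking RA against RB is also a crude answer to whether MF+ICB is more cost-effective than MF+SOC. Comparator wording is loose across the document: section 3.2 calls Arm B the control condition, and the cost definition in 9.1 is broad. The omission may be drafting and not intent. This is the economic aim, and no clinical inference or data collection depends on it.

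Much of this stands. A reader might infer that half the hypothesis will have no result at all. The documents do not support that, since the ranking and the increments would exist. A reader might also infer that the plan overstates cost-effectiveness by a factor of two. That is unsupported too: costs are absent, the effect steps are planning values, and even the direction depends on whether RB is below RA.

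What does not stand is the idea that the plan already covers the contrast. It does not say that subtraction will be done or reported. The one-way, multi-way, threshold and probabilistic sensitivity analyses vary parameters and add no comparator. Net benefit is mentioned only with currency conversion and names no contrast.

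**Conclusion.** The concern holds as a gap in the specified analysis. Aim 3 states a hypothesis against MF+SOC and SOC, defines its effect increment and final ICERs against SOC alone, and so leaves out the trial's only randomised contrast as a planned result. The GDP-per-capita label has no stated comparator. This is more than missing detail, because the rule as written rests every reported ICER on a non-randomised arm.

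The size is unknown. The label for MF+ICB against SOC can be too favourable for the value of adding community care when MF+SOC has the lower ratio against SOC. When it has the higher ratio, the planned MF+ICB versus SOC figure is also what a full incremental analysis would give. These statements assume positive effects for both options, MF+ICB more effective than MF+SOC, and a common Arm C in both contrasts. The gap should be closed, but it does not touch the primary endpoint or data collection.

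**What to change.** In section 9.2, define the cost and effect increments for MF+ICB versus MF+SOC directly from the randomised arms, and list that ICER as a planned result. Give it uncertainty that respects microfinance-group clustering and the county stratification stated in the Summary, for example by resampling whole groups within arm and county. Addendum item 9 gives 10 + 10 + 11 + 8 + 15 + 3 = 57 randomised groups.

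Alongside it, present the three options in order of cost, with simple and extended dominance applied. Report the randomised ratio in every case, since dominance rules could otherwise remove it from the table. State which comparator the GDP-per-capita thresholds apply to. Keep the SOC-based ICERs, labelled as non-randomised comparisons.

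This needs no new data: one added contrast, a cluster-level uncertainty step and a few sentences. The ratio for community care may come out less favourable. Addendum item 10 describes the outcome analysis as already carried out, so the addition should be labelled post hoc if it is made after outcome results were known.

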10.1.1 Adequacy of protection against risks

10.1.2 Informed consent

Informed consent will be written consent for participation in the trial and in the qualitative interviews. Written informed consent will be obtained by trained study staff in a private place in or near the regularly scheduled MF group (for trial participants) or the AMPATH clinic (for SOC participants and

clinic personnel involved in the qualitative interviews). Informed consent documents will be translated into Swahili or other local language and back-translated for accuracy. Informed consent will be read aloud to participants and they will be given the opportunity to ask questions before agreeing to participate. The participants will have the opportunity to read the form and take as much time as they need to do so. The participants will be offered a copy of the form to keep. The interviewer or research assistant will ask the participants if they agree to take part in the study and if they agree, both will sign and date the document. If participants are not literate, they will be asked to mark the page in the presence of a witness (another study staff member so as to not violate participant confidentiality). Interviewers and counselors will document that consent was provided prior to beginning any study procedures.

Our study team has prior experience in obtaining informed consent for research and clinical trials within the cultural context of Kenya. The informed consent procedure has been designed to maximize understanding of potential risks. Participants may decline to participate at any point.

10.1.3 Maintaining privacy and avoiding stigmatization

In order to minimize potential risk of stigma, our recruitment will occur during regularly occurring microfinance meeting times. We expect that this technique will be very effective at minimizing any attention that may be paid to study participants due to the presence of our study staff in the village. We will only discuss the nature of the study with the study participants and will train field staff to appropriately respond to queries about study activities from individuals not enrolled in the study. Study visits to the regularly scheduled microfinance group meetings will occur in unmarked vehicles in order to reduce the unlikely possibility of stigmatizing study participants.

Every effort will be made to ensure that privacy is maintained during the ICB care delivery visits in the intervention groups. All data collected during Aims 1 and 2 will be de-identified as described in the Data Safety and Monitoring Plan.

10.1.4 Minimizing psychological discomfort

In order to minimize risks from psychological discomfort or potential loss of confidentiality, potential participants will have study procedures fully explained before giving consent, with explanations about the potential risks involved in participation. All participants will have the opportunity to ask questions prior to consenting to participate. While we expect this strategy to be effective in minimizing psychological discomfort due to study procedures, we will offer referrals to mental health services offered at AMPATH for any participant in need. In cooperation with the Department of Psychiatry at Moi University School of Medicine and Moi Teaching and Referral Hospitals, AMPATH holds a special weekly clinic to meet the mental health needs of patients. Patients can be referred from any site for evaluation and treatment. A mental health nurse also provides onsite counseling one day per week at rural clinics at Mosoriot, Burnt Forest, and Turbo. The weekly clinics and onsite counseling provide treatment to patients with a variety of disorders, including depression, psychosis, and substance abuse.

